8.3. Medical History

A summary of relevant medical history and concomitant diseases will be presented by system organ class (SOC) and preferred term (PT) according to the Medical Dictionary for Regulatory Affairs (MedDRA) version 23.1 or higher, using frequency distributions (counts and percentages).

8.4. Prior Psoriasis Therapy

Prior Psoriasis therapy are summarized descriptively by treatment arm for the following:

- Number of prior conventional systemic therapies
- Number of failed prior conventional systemic therapies for subjects who had prior conventional systemic therapies
- Number of prior systemic therapies
- Number of failed prior systemic therapies for subjects who had prior systemic therapies

Apremilast**Statistical Analysis Plan. Protocol CC-10004-PSOR-020****Amgen INC.**

- Number of prior biologic therapies
- Number of failed prior biologic therapies for subjects who had prior biologic therapies
- Number of prior topical therapies
- Number of failed prior topical therapies for subjects who had prior topical therapies
- Number of prior photo therapies
- Number of failed prior photo therapies for subjects who had prior photo therapies

8.5. Prior and Concomitant Procedures

Prior and concomitant procedures will be coded using the MedDRA Version 22.1 or higher.

8.5.1. Prior Procedures

Prior procedures are defined as those started before the start of the study treatment (whether or not ended before the start of the study treatment) at the time of randomization.

A frequency tabulation of the number of subjects with each previous procedure will be given for the ITT population by treatment arm, system organ class (SOC), and preferred term (PT).

8.5.2. Concomitant Procedures

Concomitant procedures that started during each of the following three study phase/period are summarized by SOC and PT: (1) Placebo-controlled Phase (Weeks 0 to16) using safety population by treatment, (2) Apremilast Exposure Period using Apremilast Exposure Population and (3) Observational Follow-up Phase for subjects who entered this phase.

The Anatomical Therapeutic Chemical (ATC) coding scheme of the World Health Organization Drug Dictionary (WHO DD version DDE B3 March 2019 or higher) is used to group the prior and concomitant medications into the WHO therapeutic drug class (ATC2 level) and generic drug name.

8.5.3. Prior Medications

Only prior medications that are not discontinued at or before the time of consent are collected. Prior medications are defined as medications that were started before the start of the study treatment at the time of randomization and ended before the start of the study treatment. Medications initiated prior to the start of study treatment and continued after the start of study treatment are counted as both prior and concomitant medications.

The number (%) of subjects receiving at least one prior medication are summarized for the ITT population by treatment arm, ATC2 level, and standardized medication name.

Note that the prior psoriasis medications are summarized along with other baseline characteristics and not included in the prior medication summary.

8.5.4. Concomitant Medications

Concomitant medications are defined as non-study medications started during a study phase/period of interest or started before the study phase/period of interest but ended or remain ongoing during this study phase/period.

The number (%) of subjects receiving at least one concomitant medication, the number (%) of subjects receiving at least one medication within a relevant category, and each concomitant medication are summarized for (1) Placebo-controlled Phase (Weeks 0 to 16) using safety population by treatment, (2) Apremilast Exposure Period using Apremilast Exposure Population, and (3) Observational Follow-up Phase for subjects who entered this phase.

8.6. Study Treatment Duration

Study treatment duration in weeks is calculated as (the date of the last dose of study treatment – the date of the first dose of study treatment + 1) / 7 and rounded to one decimal place for each subject for a given analysis phase/period.

Study treatment duration will be summarized based on the safety population for the Placebo-Controlled Phase (Weeks 0 to 16) by treatment and based on the Apremilast Exposure Population for the Apremilast Exposure period.

Summary statistics for treatment duration as well as a frequency summary of treatment duration categories specified in Table 4 will be provided.

Table 4 Definitions of time intervals used to summarize exposure to study Medication

Duration category	Duration in terms of days
Placebo-Controlled Phase	
<4 weeks	<28 days
≥ 4 to < 8 weeks	≥ 28 to < 56 days
≥ 8 to < 12 weeks	≥ 56 to < 84 days
≥ 12 to < 16 weeks	≥ 84 to < 112 days
≥ 16 weeks	≥ 112 days
Apremilast Exposure period	
≥ 4 weeks	≥ 28 days
≥ 8 weeks	≥ 56 days
≥ 12 weeks	≥ 84 days
≥ 16 weeks	≥ 112 days
≥ 20 weeks	≥ 140 days
≥ 24 weeks	≥ 168 days
≥ 28 weeks	≥ 196 days
≥ 32 weeks	≥ 224 days
≥ 36 weeks	≥ 252 days
≥ 40 weeks	≥ 280 days
≥ 44 weeks	≥ 308 days
≥ 48 weeks	≥ 336 days
≥ 52 weeks	≥ 364 days

Apremilast

Statistical Analysis Plan. Protocol CC-10004-PSOR-020

Amgen INC.

The treatment duration is from the first non-zero dose and the last non-zero dose of the study treatment recorded on the study drug exposure form for the corresponding study phase/period.

A subject data listing of study drug records including the reasons for missed dose will be provided.

8.7. Treatment Compliance

Summaries on the compliance rate are provided based on the ITT population for the Placebo-Controlled Phase (Weeks 0 to 16) and the Apremilast Extension Phase (Weeks 16-52) for subjects who entered the Apremilast Extension Phase by treatment.

The treatment compliance (in %) for each subject will be computed as 100 times the total number of tablets taken (the total number of tablets dispensed minus the total number of tablets returned) over the analysis phase of interest divided by the intended total number of tablets that should have been taken over the same phase. The algorithm on how the intended total number of tablets is calculated is provided in Appendix 15.3.

Of note, compliance rate will not be calculated for subjects (if exist) who have only the dispense record at Week 0/Visit 2 and no other drug accountability records.

Both the summary statistics for compliance rate (%) and a frequency summary with the following categories: <75%, 75% to 120%, and >120% are provided. A subject data listing of drug accountability records is also provided.

9. EFFICACY ANALYSIS

9.1. General Approaches to Efficacy Analysis

All efficacy evaluations will be conducted using the ITT population. Supplemental analysis of the primary efficacy endpoint using the PP population will be conducted.

The summary and analyses of the primary and secondary endpoints evaluated at or prior to Week 16 will be performed by treatment (placebo vs. apremilast 30 mg BID). Statistical comparisons will be made between apremilast 30 mg BID and placebo; the null hypothesis is that the effects of the two treatments (i.e., placebo vs. apremilast 30 mg BID) have no difference.

Descriptive statistics (n, mean, stdev, median, Q1, Q3, min, max) will be presented for appropriate endpoints at specified time points. Specifically, for continuous variables, descriptive statistics for baseline and change (or percentage change) from baseline will be provided.

Categorical variables will be summarized with frequency tabulations at baseline or by time point; shift tables will be provided when appropriate.

For the primary and the secondary efficacy endpoints during the Double-blind Placebo-controlled Phase, the following analysis will be performed:

- For binary endpoints, missing data from the original continuous-like score will be handled by multiple imputation (MI) as the primary approach. The response variable will then be derived based on the continuous score. Statistical outputs from each of the imputed complete data sets will be combined in making statistical inferences. For the combined inference, the response rates for each treatment arm and differences for treatment comparison were the averages from the 25 imputed data sets. The response rate and its 95% confidence interval (CI) will be calculated by treatment. The difference of the response rate (Apremilast 30 mg BID - placebo) and its 95% CI as well as the p-value will be produced using the Cochran-Mantel-Haenszel (CMH) test and adjusting for the stratification factor at randomization (i.e., the manifestations of scalp psoriasis, nail psoriasis, palmoplantar psoriasis, genital psoriasis, or psoriasis in visible locations). SAS PROC FREQ with the COMMONRISKDIFF (TEST=MH) option will be used for the analysis.
- For continuous endpoints, the primary approach for handling missing data will be the multiple imputation (MI) method. Data will be analyzed using the analysis of covariance (ANCOVA) model with baseline values, treatment group and stratification factors (i.e., the manifestations of scalp psoriasis, nail psoriasis, palmoplantar psoriasis, genital psoriasis, or psoriasis in visible locations) as independent variables. SAS Proc Mixed will be used for the analysis. The least square mean (LS mean) with 95% CI for each treatment and difference of LS mean (Apremilast 30 mg BID - placebo) with 95% CI as well as the p-value will be provided.

Efficacy results will be considered statistically significant after consideration of the strategy for controlling the Type I error rate that is described in Section **Error! Reference source not found.** All statistical tests will be two-sided and be conducted at the 0.05 significance level, and p-values will be reported. For the efficacy endpoints evaluated after Week 16, only the treatment effect

Apremilast**Statistical Analysis Plan. Protocol CC-10004-PSOR-020****Amgen INC.**

estimates and the corresponding 95% confidence intervals (CIs) within each treatment arm will be provided to show the long-term treatment profile. No between group comparison will be conducted. Time plots on response rate or mean change (percent change) from baseline by treatment over the Placebo-controlled Phase and the Apremilast Extension Phase will be provided to show the maintenance of the treatment effect over time.

Data listings for quality of life assessments and efficacy assessments over the Placebo-controlled Phase and the Apremilast Extension Phase will be provided. An analysis phase flag will be included in each listing to indicate the phase that a record belongs to.

9.2. Multiplicity

The primary and some secondary efficacy endpoints will be hierarchically ranked for testing in order to control the overall type I error rate in claiming statistical significance at the 2-sided 0.05 significance level. Specifically, for the primary efficacy endpoint (DLQI response at Week 16), if the 2-sided p-value from the comparison between Apremilast 30 mg BID and placebo is below 0.05, the outcome will be considered statistically significant and Apremilast 30 mg BID will be declared effective. For any secondary endpoint, statistical significance will be claimed only if its 2-sided p-value is below 0.05 and tests for the primary endpoint and all previous secondary endpoints are significant at the 2-sided 0.05 level. The proposed test sequence for the primary and some secondary efficacy endpoints is listed as the following:

- Achieving DLQI response at Week 16 (defined as ≥ 4 -point reduction in DLQI from baseline at Week 16) from baseline in DLQI at Week 16
- Change from baseline in DLQI at Week 16
- Percent change in Body Surface Area (BSA) affected by psoriasis at Week 16
- Change from baseline in Pruritus Numeric Rating Scale (NRS) score at Week 16
- Change from baseline in skin discomfort/pain Visual Analog Scale (VAS) at Week 16
- Achieving Psoriasis Area Severity Index (PASI) < 3 at Week 16
- Achieving Patient Benefit Index (PBI) global score of ≥ 1 at Week 16
- Percent change from baseline in European Quality of Life 5-Dimension (EQ-5D) score at Week 16
- Change in Work Productivity and Activity Impairment Questionnaire: Psoriasis (WPAI: PSO) domain scores at Week 16

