4.2.5.8. The Work Productivity and Activity Impairment Questionnaire: Psoriasis (WPAI: PSO)

The WPAI: PSO questionnaire is a validated, 6-item self-administered instrument used to assess the impact of disease on work productivity in psoriasis due to specified health problem during the last 7 days. The 6 questions are: Q1 = currently employed; Q2 = hours missed due to problems associated with psoriasis; Q3 = hours missed other reasons; Q4 = hours actually worked; Q5 = degree health affected productivity while working (using a 0 to 10 Visual Analogue Scale (VAS)); Q6 = degree health affected productivity in regular unpaid activities (VAS) [Reilly, 2012] The sum of work time missed and work impairment while working yielded the overall work impairment measure. Four types of scores were calculated as following. All scores were expressed as percentages, with higher scores indicating greater impairment.

- 1) percent work time missed due to health = $Q2/(Q2 + Q4)$ for those who were currently employed;
- 2) percent impairment while working due to health = $Q5/10$ for those who were currently employed and actually worked in the past seven days;
- 3) percent overall work impairment due to health $Q2/(Q2 + Q4) + ((1 - Q2/(Q2 + Q4)) \times (Q5/10))$ for those who were currently employed. For those who missed work and did not actually work in the past seven days, the percent overall work impairment due to health will be equal to the percent work time missed due to health;
- 4) percent activity impairment due to health $Q6/10$ for all respondents.

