4.4. Sample Size Determination

For the primary endpoint, i.e., the response rate (π) defined as the proportion of subjects achieving a ≥ 4 -point reduction from baseline in DLQI at Week 16, the superiority of Apremilast 30 mg BID versus placebo will be tested. The hypotheses on superiority are defined as:

$$H_0: \pi_{APR} - \pi_{PBO} = 0$$

versus

$$H_1: \pi_{APR} - \pi_{PBO} > 0$$

Using an exploratory analysis on a subset of subjects meeting the following criteria: a) ScPGA ≥ 3 or b) NAPSI ≥ 1 or c) PPPGA ≥ 3 at baseline and DLQI ≥ 10 at baseline in the PSOR-008 and PSOR-009 Phase 3 studies, it was estimated that the proportion of subjects who achieved a ≥ 4 -point reduction from baseline in DLQI was 0.50 (97 responders out of 193 subjects) and 0.83 (337 responders out of 406 subjects) for placebo and Apremilast 30 mg BID, respectively.

Assuming a placebo DLQI responder proportion of 0.50 at Week 16, a minimum total sample size of 210 subjects (140 allocated to Apremilast 30 mg and 70 allocated to placebo) is needed to detect a 0.20 difference in the DLQI responder rate between Apremilast and placebo with at least 0.807 power using a two-sided test at the 0.05 level of significance. This sample size calculation is based on an unpooled variance, and determined using the commercial software EaST, Version 6.3. Allowing for an 24% discontinuation rate prior to Week 16, the sample size of 276 subjects should be sufficient.

5. GENERAL STATISTICAL CONSIDERATIONS**5.1. Reporting Conventions**

- The statistical test on the primary endpoint is at a 2-sided 0.05 significance level, any p-values reported for other endpoints are considered as summary statistics;
- P-values are rounded to 4 decimal places. P-values that round to 0.0000 are presented as '<0.0001' and p-values that round to 1.000 are presented as '>0.9999';
- Confidence intervals (CIs) are presented as 2-sided 95% CIs;
- Summary statistics consist of the number and percentage of subjects in each category for discrete variables, and the sample size, mean, median, Standard Deviation (STDEV), minimum, and maximum for continuous variables;
- All mean and median values are formatted to one more decimal place than the measured value, standard deviation values are formatted to two more decimal places than the measured value, minimum and maximum values are presented to the same number of decimal places as the measured value, and the 95% CI are formatted to two more decimal places than the measured value;

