Mean change in Work Productivity and Activity Impairment Questionnaire: Psoriasis (WPAI: PSO) domain scores** at Week 16	ANCOVA model adjusted by baseline Psoriasis WPAI score**, treatment, stratification factor on data collected on scheduled Week 16 visit	ANCOVA model adjusted by baseline Psoriasis WPAI score**, treatment, stratification factor on end of phase assessment
*two variables will be evaluated individually: EQ-5D VAS and EQ-5D index value		
**four variables will be evaluated individually: percentage work missed, work impairment, overall work impairment, and activity impairment		

For each continuous-like efficacy assessments, the SAS procedure MI will be used to impute missing values for each scheduled visit in the Placebo-controlled Phase (Weeks 0 to 16). There are exceptions for the EQ-5D assessment and WPAI: PSO assessment, which are only assessed at Week 16/discontinuation visit in the Placebo-controlled Phase. For these two endpoints, no missing data imputation will be conducted and the analyses will be conducted on assessments collected at the scheduled Week 16 visit as well as on assessments collected at end of phase (section 5.5).

For MI, the missing data patterns will be checked by treatment and stratification factor at Baseline (Week 0), and Weeks 2 (if applicable), 4, and 16. If there are non-monotone missing patterns, two separate imputation procedures will be used to complete the imputation process. In case of convergence issue, same strategy as for the primary endpoint will be followed.

In the first step, the Markov Chain Monte Carlo (MCMC) method will be used to impute missing data by baseline value, treatment and stratification factor to create M=25 imputed data sets with monotone missing patterns. The minimum and the maximum values for imputation will set depending on the range of the corresponding score of interest. The seed will be set to 804529, the imputed values will be rounded to integers and a single chain will be used to produce imputations. This step will be skipped if the data missing pattern is monotone.

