12. INTERIM ANALYSIS

No interim analysis will be conducted. No DMC is planned for this study either.

For publication purpose, analyses on the data up to the primary timepoint of Week 16 are planned based on a Week 16 data transfer after all subjects have completed the Week 16 Visit (or discontinued from the study). However, unblinded data will only be made available to selected Sponsor and Contract Research Organization (CRO) team members involved with Week 16 data analysis and publication preparations. All other Sponsor, site, and CRO personnel directly involved with the conduct of the study, will remain blinded to treatment assignments until the final database lock at the final study completion. After all subjects have completed the Observational Follow-up Phase following the Week 52/discontinuation visit in the Apremilast Extension Phase (Weeks 16 to 52), the final database will be locked and transferred for all analyses planned in this SAP, based on which, a Clinical Study Report will be generated.

**13. CHANGES TO THE STATISTICAL ANALYSES SECTION OF
THE PROTOCOL**

In order to control the overall type I error rate, the multiplicity adjustment is made to the primary endpoint and some secondary endpoints by following the hierarchical rank for testing in Section 9.2. This is deviated from Section of 9.6.5 in the protocol, where no multiplicity adjustment is planned.

Per-protocol (PP) population includes all subjects who are in the ITT population, who receive at least one dose of IP, have both baseline and at least one post-treatment DLQI evaluation, and have no major protocol deviations which may affect analyses in the Placebo-controlled Phase. This definition is deviated from Section 5.3.2 in the protocol.

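### SAP 9.2 claims overall type I error control, but its EQ-5D and WPAI steps hold two and four separately tested variables with no rule for what counts as a pass

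*SAP*

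**What the plan says.** SAP 9.2 sets out a fixed sequence of nine Week 16 endpoints: DLQI response (primary), DLQI change, BSA, itch NRS, pain VAS, PASI below 3, PBI of at least 1, EQ-5D and WPAI: PSO. The purpose given is "in order to control the overall type I error rate in claiming statistical significance at the 2-sided 0.05 significance level". A secondary endpoint may be claimed only if its own p-value is below 0.05 and "tests for the primary endpoint and all previous secondary endpoints are significant at the 2-sided 0.05 level".

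The footnotes to Table 5 in SAP 9.4.1 add that for EQ-5D "two variables will be evaluated individually: EQ-5D VAS and EQ-5D index value", and for WPAI: PSO "four variables will be evaluated individually: percentage work missed, work impairment, overall work impairment, and activity impairment". SAP 9.1 states: "All statistical tests will be two-sided and be conducted at the 0.05 significance level".

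SAP Section 13 declares the hierarchy as a deliberate departure from protocol 9.6.5, which planned no multiplicity adjustment. It says the adjustment covers the primary and "some secondary endpoints by following the hierarchical rank for testing in Section 9.2". SAP 5.1 nevertheless still says that "any p-values reported for other endpoints are considered as summary statistics".

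**The concern.** A fixed sequence controls error because each step is one hypothesis with one pass-or-fail result. Steps 8 and 9 do not have that form. With two EQ-5D results and four WPAI results, the SAP leaves two questions open:

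- **What supports a claim within the step?** It could be any one variable, all of them, or a lead variable.
- **What opens WPAI if the EQ-5D VAS and index disagree?** The requirement that all previous endpoints be significant suggests both must pass. But SAP 9.2 lists EQ-5D as a single endpoint, so this is not explicit.

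One favourable score out of two or four could therefore be reported as a type-I-error-controlled finding. The rule could also be settled after the Week 16 results are known, since selected sponsor and CRO staff are unblinded for that analysis and it may be published before the study ends.

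**Working it through.** **Inputs.** Two-sided 0.05 per test (SAP 9.1, 9.2); two EQ-5D and four WPAI variables (Table 5 footnotes); WPAI scoring (SAP 4.2.5.8). The documents give no correlations between the variables, so every correlation below is an assumption.

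**1. The plan's own figure.** With one hypothesis per step, any false claim requires rejecting the first true null in the order. That null is tested once, at 0.05, so the overall error is at most 0.05. This reproduces the claim for steps 1 to 7.

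**2. Steps 8 and 9 when any one significant variable counts.** Conditions: all variables in the step are null and all earlier steps have passed. Under independence:

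- EQ-5D: 1 − 0.95² = 0.0975
- WPAI: 1 − 0.95⁴ = 0.1855

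If every variable in the step must be significant, the same conditions give 0.05² = 0.0025 and 0.05⁴ = 0.000006.

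With equally correlated normal test statistics (2,000,000 draws, |Z| > 1.96):

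| Assumed correlation | EQ-5D, any of 2 | EQ-5D, both | WPAI, any of 4 | WPAI, all 4 |
|---|---|---|---|---|
| 0 | 0.0975 | 0.0025 | 0.186 | <0.0001 |
| 0.3 | 0.095 | 0.005 | 0.174 | 0.0002 |
| 0.5 | 0.091 | 0.009 | 0.156 | 0.0015 |
| 0.7 | 0.084 | 0.017 | 0.130 | 0.006 |
| 0.9 | 0.070 | 0.030 | 0.094 | 0.019 |

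**3. WPAI with its formula built in.** Four independent tests are impossible here. SAP 4.2.5.8 says "The sum of work time missed and work impairment while working yielded the overall work impairment measure", and its formula is overall = A + (1 − A) × P, where A is the share of work time missed and P the impairment while working. The 18.5% is therefore only an upper value. If the derived score added no separate chance of error, three independent tests would give 1 − 0.95³ = 0.143.

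A simulation used this formula with 140 versus 70 subjects, 70% employed (assumed), 60% of those with no absence (assumed), 6,000 null trials and each test calibrated to 5%. P(any significant) was 0.150, 0.144, 0.139, 0.124 and 0.108 at latent correlations of 0, 0.3, 0.5, 0.7 and 0.9. The simulation error at 0.15 is √(0.15 × 0.85 / 6,000) = 0.005. Varying the assumptions (50–90% employed, 40–85% without absence) gave roughly 9% to 16%.

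**4. The gate into WPAI.** Suppose one significant EQ-5D variable were enough to open WPAI, one EQ-5D variable had a real effect almost certain to be detected, and the other EQ-5D variable and all four WPAI scores were null. Five null tests would then be exposed: 1 − 0.95⁵ = 0.226. This is again an independence figure that the WPAI formula rules out as an actual value.

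**5. Rules that restore control.** A fixed order with each variable at 0.05 gives at most 0.05, and so does requiring all variables in a step. Splitting alpha within the step gives 1 − 0.975² = 0.0494 for EQ-5D and 1 − 0.9875⁴ = 0.0491 for WPAI under independence, and never more than 0.05. WPAI must then open only if both EQ-5D variables are significant.

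**The case against.** The best defence is that the SAP can be read conservatively. The sentence in SAP 9.1 just before the one quoted makes significance subject to the multiplicity strategy, so 9.1 does not by itself license separate claims at 0.05. The Table 5 footnotes sit in a table of models and may mean only that each variable gets its own ANCOVA. On that reading an endpoint passes only if all its variables pass, and control holds.

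The reading is possible, and it is why the fault is an unwritten rule and not a procedure that must break 0.05. It does not close the gap. The 9.1 sentence points back to the 9.2 strategy, which is where the rule is missing. Nothing states that all variables must pass, and evaluating them individually leans the other way.

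Two further points limit the weight. The inflated rates need real effects at the earlier steps: if every null were true, including the primary, the primary test alone would hold overall error at or below 5%. And these are the last two of nine steps, so nothing else depends on them. Both points stand. But overall control has to hold when some effects are real, and those are the circumstances in which steps 8 and 9 are reached.

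The SAP 5.1 sentence about summary statistics does not help either. Section 13 replaces that approach, so it is an editorial leftover, separate from the within-step gap.

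**Conclusion.** The concern holds, and it is limited to steps 8 and 9. The primary endpoint and the first six secondary steps keep their control at 0.05.

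For the last two steps the stated control depends on a claim rule that is not written. On the least favourable reading, with the conditions in step 2 of the working, the false-claim rate is 7.0% to 9.75% for EQ-5D over assumed correlations from 0.9 down to 0. For WPAI it is about 11% to 15% over the same range in the formula-based simulation, which also rests on assumed employment and absence rates. Any correlation short of perfect gives more than 5%. On the all-must-succeed reading both steps stay at or below 5%.

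This should be corrected, but it does not threaten the trial's main conclusion.

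**What to change.** Before the Week 16 data transfer, amend SAP 9.2 in one of these ways:

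- **Preferred:** list the two EQ-5D and four WPAI variables as separate steps in a stated order, so the sequence runs from step 1 to step 13 (7 + 2 + 4). The existing gate in 9.2 then also settles that both EQ-5D variables must pass before WPAI opens.
- **Or** name one EQ-5D and one WPAI variable for the hierarchy and make the other four descriptive.
- **Or** write a within-step rule for both: both EQ-5D variables must be significant before any EQ-5D claim and before WPAI opens, and Holm is applied across the four WPAI scores.

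Separately, align SAP 5.1 with 9.2 and Section 13, so that only p-values outside the hierarchy are called summary statistics.

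The cost is SAP wording and slightly fewer possible claims on EQ-5D and WPAI. Data collection, sample size and the primary analysis do not change.
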